Bone marrow aspiration to be performed to confirm a CR and as clinically indicated. In case of dry-tap, bone marrow biopsy to be performed to confirm CR. Once CR is confirmed at a given time point, a consecutive assessment for immunofixation and free light chain is required.
22. Extramedullary Disease: Baseline to be performed within 21 days prior to study drug administration. If extramedullary disease present at baseline, to be performed approximately every 12 weeks (eg. at Cycle 4, 7, 10). To be performed upon clinical suspicion of progressive disease. This may include computerized tomography (CT) or magnetic resonance imaging (MRI) scan of the abdomen/pelvis, CT or x-ray of the chest, ultrasound of the liver/spleen or abdomen. May be omitted at End of Treatment if conducted within 12 weeks. All imaging will be sent to a central imaging lab.
23. Disease assessments during follow-up period are only required for patients with PR or better who have discontinued study treatment for reasons other than disease progression and have not yet started treatment with another anti-cancer therapy. Patients will be followed every 4 weeks for progression during this period. Disease assessments required every 4 weeks is myeloma-specific lab tests. Extramedullary disease assessment is required approximately every 12 weeks or upon clinical suspicion of progressive disease. All imaging will be sent to a central imaging lab. A bone marrow aspiration and/or biopsy, skeletal survey are only required if clinically indicated to confirm response or progression according to IMWG criteria.
Disease assessments not required once patient starts treatment with another anti-cancer therapy.
24. Skeletal survey and chest X-ray: X-ray to be performed at screening on all patients (the same methods must be used throughout the study). Repeat skeletal surveys are only required as clinically indicated. All imaging will be sent to a central imaging lab.
X-ray skeletal survey should include radiographs of the following: lateral skull; Postero-Anterior (PA) chest; Antero-Posterior(AP) and lateral cervical spine; AP and lateral thoracic spine; AP and lateral lumbar spine; AP pelvis; AP upper extremities, shoulder to elbow, bilateral; and AP lower extremities, hip to knee, bilateral.
Chest X ray: To be performed at screening for assessment of pulmonary disease condition and then as clinically indicated.

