6.9.2 Independent Adjudication Committee

The Independent Adjudication Committee (IAC) will be responsible for objectively assessing clinical response as defined by the IMWG response criteria on an ongoing basis in order to independently evaluate the drug effect of isatuximab on disease status.

The IAC will be comprised of multiple independent MM experts. They will be responsible for:

- Objectively assessing clinical response as defined by the IMWG response criteria on an ongoing basis in order to independently evaluate the drug effect of isatuximab on disease status
- The IAC will determine response using:
 - Serum and urine M-protein, free light chains (FLC), bone marrow aspirate/biopsy and corrected calcium
 - Radiologic results for bone lesions and plasmacytoma assessment

Detailed guidelines regarding the structure, function and decision-making mechanisms for this committee are described in the IAC charter.

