9.3 EFFICACY

9.3.1 Criteria for Response

ORR is defined as the proportion of patients with stringent complete response (sCR), complete response (CR), very good partial response (VGPR), and partial response (PR) based on responses as assessed using the International Myeloma Working Group (IMWG) Uniform Response Criteria (see [Appendix C](#)). Response evaluation will be performed on a monthly basis. The best overall response for each patient will be determined by independent adjudication committee.

All responses (sCR, CR, VGPR, PR) should be confirmed on 2 consecutive laboratory efficacy parameters assessments according to study flow-chart (approximately 4 weeks interval). Stable disease (SD) does not require confirmation. Disease progression by paraprotein should be confirmed on within the first 4 weeks after last assessment. Disease progression based on imaging, bone marrow plasma cell percentage, or hypercalcemia (not attributable to any other cause) do not need to be confirmed.

Clinical benefit rate (CBR): defined as the proportion of patients with sCR, CR, VGPR, PR or MR according to IMWG criteria.

Duration of response (DOR): defined as the time from the date of the first response to the date of subsequent progressive disease (PD) or death, whichever happens earlier. In the absence of the confirmation of subsequent disease progression or death before the analysis cut-off date, the DOR will be censored at the date of the last valid assessment performed before the analysis cut-off date or date of initiation of new anticancer treatment, whichever is earlier. DOR is determined only for

patients who have achieved a response of \geq PR. DOR will not be calculated for patients that do not achieve a response.

Overall survival (OS): defined as the time interval from the date of first study treatment administration to death due to any cause. In the absence of the confirmation of death before the analysis cutoff date, OS will be censored at the last date the patient is known to be alive or at the study cutoff date, whichever is earlier.

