PD	Increase of $\geq 25\%$ from lowest response value in any one of the following: 
Serum M-component (the absolute increase must be ≥ 0.5 g/dL) and/orUrine M-component (the absolute increase must be ≥ 200 mg/24 h) and/orOnly in patients without measurable serum and urine M-protein, the difference between involved and uninvolved FLC levels. The absolute increase must be >10 mg/dLOnly in patients without measurable serum and urine M-protein and without measurable disease by FLC levels, bone marrow plasma cell percentage (absolute % must be $\geq 10\%$)Definite development of new bone lesions or soft tissue plasmacytomas or definite increase in the size of existing bone lesions or soft tissue plasmacytomasDevelopment of hypercalcemia (corrected serum calcium >11.5 mg/dL) that can be attributed solely to the plasma cell proliferative disorder

All response categories (CR, sCR, VGPR, PR and PD) require two consecutive assessments made at any time before the institution of any new therapy; complete response and PR and SD categories also require no known evidence of progressive or new bone lesions if radiographic studies were performed. VGPR and CR categories require serum and urine studies regardless of whether disease at baseline was measurable in serum, urine both or either. Radiographic studies

are not required to satisfy these response requirements. Bone marrow assessments need not be confirmed. For progressive disease, serum M-component increases of ≥ 1 g/dL are sufficient to define response if starting M-component is ≥ 5 g/dL.

IMWG clarification for coding PD: Clarified that Bone marrow criteria for PD are to be used only in patients without measurable disease by M protein and by FLC levels. Clarified that 25% increase refers to M protein, FLC, and bone marrow results and does not refer to bone lesions, soft tissue plasmacytomas or hypercalcemia. Note the lowest response value does not need to be a confirmed value.

Table 10 - Additional response criteria for specific disease states

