#### **2.1.3 Efficacy endpoints**

Response assessments were to be performed on a monthly basis using IMWG criteria (Rajkumar. 2011) and included:

- M-protein quantification (serum and 24-hr urine)
- Serum free light chain levels
- Corrected serum calcium

In case of plasmacytoma at baseline, radiological evaluations were to be performed every 3 cycles or when clinically indicated (i.e., to confirm a progression).

In case of bone lesions at baseline, bone lesion evaluations were to be performed when clinically indicated or to confirm a response or progression. Bone marrow biopsy/aspiration was to be performed to confirm a sCR or CR.

An independent adjudication committee (IAC) independently assessed clinical response using the IMWG response criteria.

Biological responses ( $\geq$ PR) and progression were to be confirmed on 2 consecutive biological (serum and/or urine M protein) disease assessments. No confirmation was required for radiological assessment.

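### Protocol Appendix C and section 9.3.1 disagree on whether progression by imaging or hypercalcemia needs a second assessment, and the Phase 2 SAP answers this for imaging only

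*Protocol*

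**What the plan says.** Protocol Appendix C, in the paragraph under its response table, states: "All response categories (CR, sCR, VGPR, PR and PD) require two consecutive assessments", both to fall before new therapy starts. The PD row above that paragraph includes new or growing bone lesions and plasmacytomas, and hypercalcemia. The paragraph makes one exemption from confirmation: "Bone marrow assessments need not be confirmed".

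Protocol 9.3.1 treats the routes to progression differently. For M-protein: "Disease progression by paraprotein should be confirmed on within the first 4 weeks after last assessment". For the others: "Disease progression based on imaging, bone marrow plasma cell percentage, or hypercalcemia (not attributable to any other cause) do not need to be confirmed".

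Phase 2 SAP 2.1.3 asks for two consecutive serum or urine M-protein assessments for biological progression, then adds: "No confirmation was required for radiological assessment". It says nothing about hypercalcemia. Section 2.1.3.2 takes DOR to IAC-determined PD and PFS to IAC-confirmed progression. Protocol 9.3.1 counts the first assessed progression for PFS and TTP.

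Protocol 6.9.2 makes the IAC responsible for "clinical response as defined by the IMWG response criteria". The only such criteria printed in the protocol are those in Appendix C, and 9.3.1 itself refers to that appendix.

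**The concern.** The IAC decides what is PD, and the SAP analyses what the IAC returns. An IAC member working from Appendix C could withhold PD for a new bone lesion, a new plasmacytoma or hypercalcemia documented once. A member working from 9.3.1 would call PD on the same facts. In the first case, if nothing is repeated before new therapy and the patient does not die first, Phase 2 SAP 2.1.3.2 censors PFS and DOR at the last assessment that did not show progression. That censoring is informative, because it falls on patients who have just progressed. It moves PFS and DOR upward, and also TTP as the protocol defines it. For TTP, death does not restore an event.

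**Working it through.** **Step 1. The rules by route of progression.**

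| Route | Appendix C | Protocol 9.3.1 | Phase 2 SAP 2.1.3 |
|---|---|---|---|
| Serum or urine M-protein | two assessments | confirm | two assessments |
| Imaging | two assessments, no exemption | no confirmation | no confirmation |
| Hypercalcemia | two assessments, no exemption | no confirmation | not mentioned |
| Bone marrow | exempt | no confirmation | not mentioned |

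The two protocol sections agree on M-protein and marrow. They conflict on imaging and hypercalcemia. Appendix C also says that radiographic studies are not needed to meet its response requirements. That means imaging need not be done. It does not say that progression found by imaging counts without a repeat.

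**Step 2. Is a second assessment available?**

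- Hypercalcemia: often. Corrected calcium is part of serum chemistry on Day 1 and Day 15 of each later cycle and at End of Treatment (protocol 1.6, footnote 15; protocol 12.4).
- Imaging: not assured. Footnote 22 says: "If extramedullary disease present at baseline, to be performed approximately every 12 weeks". It also calls for imaging on clinical suspicion of progression, but that scan may be the first to show it. End of Treatment imaging may be omitted if done within 12 weeks. Skeletal surveys are repeated only when clinically indicated (footnote 24).
- After stopping for progression, no follow-up disease assessment is required (footnote 23; protocol 12.5 and 12.6). Under Appendix C both assessments must precede new therapy.

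So some of these progressions would be confirmed and some would not.

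**Step 3. Size.** The documents state no figure to reproduce. Two inputs are needed and neither is given, so both are assumptions:

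- s, the share of progressions seen by imaging or hypercalcemia alone;
- u, the fraction of those never confirmed and therefore censored.

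Take a constant hazard and treat all events as progressions. The hazard estimate is events divided by person-time. Removing a fraction s × u of events at about the same person-time multiplies the hazard by 1 − s × u, and so the median by 1/(1 − s × u). For event counts, take 33 patients, the lower end of the planned range in protocol 13.1, and assume that all progress.

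| s | u | s × u | Median multiplied by | Events lost of 33 |
|---|---|---|---|---|
| 10% | 50% | 0.05 | 1/0.95 = 1.053 | 1.65 |
| 20% | 50% | 0.10 | 1/0.90 = 1.111 | 3.3 |
| 10% | 100% | 0.10 | 1/0.90 = 1.111 | 3.3 |
| 20% | 100% | 0.20 | 1/0.80 = 1.250 | 6.6 |

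The last two rows are upper bounds for those shares. They assume that nothing is confirmed and that no death restores an event. They also place the censoring at about the event time, whereas the SAP censors earlier, which removes some person-time and lowers the inflation.

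**Step 4. Primary endpoint.** ORR counts patients whose best response is PR or better (Phase 2 SAP 2.1.3.1). How PD is confirmed does not change that count.

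**The case against.** The strongest reply is that two trial-specific texts, protocol 9.3.1 and Phase 2 SAP 2.1.3, agree that imaging progression needs no confirmation, and a general criteria appendix should yield to them. On hypercalcemia the SAP is silent but does not contradict 9.3.1, since its confirmation rule names M-protein only. Detailed IAC rules are in the IAC charter, which may already carry the 9.3.1 wording. PFS and DOR are secondary in a single-arm study, with no hypothesis test on either.

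Most of this stands as a limit on size and importance. It does not remove the conflict. No text says that 9.3.1 overrides Appendix C. If the IAC withholds PD, a sentence in the SAP cannot restore it. The term IAC-confirmed leaves open whether a repeat is required.

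A reader might infer three stronger things that the documents do not support:

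- That the conflict covers every progression, marrow included. Appendix C exempts marrow itself. Its marrow criterion for PD applies only without measurable M-protein or FLC disease, while inclusion criterion I 06 requires measurable serum or urine M-protein.
- That a second assessment is usually missing. Calcium is repeated on schedule, and imaging is also done on clinical suspicion of progression.
- That the same progression is always an event under one rule and censored under the other. Under Appendix C it still counts if repeated before new therapy, and for PFS and DOR a death before new therapy or cutoff is an event.

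**Conclusion.** The concern holds for progression by imaging and by hypercalcemia. Appendix C and 9.3.1 give opposite rules. The Phase 2 SAP sides with 9.3.1 on imaging, omits hypercalcemia, and leaves its PFS event term undefined. A literal use of Appendix C by the IAC can bias PFS, DOR and TTP upward. It is not shown that this will happen, because the charter is not among the documents.

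The size is unknown. Under the assumed shares of 10% to 20%, the exponential median rises by about 5% to 11% if half of these progressions go unconfirmed. It rises by at most about 11% to 25% if all do. The primary ORR test is unaffected. The texts should be aligned, since this fixes the event definition for the final time-to-event analysis at no cost in data.

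**What to change.** - Protocol Appendix C: limit the two-assessment requirement for PD to M-protein (and FLC where used), or refer to 9.3.1 for confirmation of progression.
- Phase 2 SAP 2.1.3: add hypercalcemia to the sentence that exempts radiological assessment.
- Phase 2 SAP 2.1.3.2: define IAC-confirmed as adjudicated by the IAC under the 9.3.1 rule.
- IAC charter: check that it uses the same wording, and change it only if it does not.

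These changes concern the endpoint definition only, not when treatment is stopped. The cost is about one sentence in each place. No new data or visits are needed.

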Appendix D Definition of Line of Therapy

A line of therapy is defined as one or more cycles of a planned treatment program. This may consist of one or more planned cycles of single-agent therapy or combination therapy, as well as a sequence of treatments administered in a planned manner. For example, a planned treatment approach of induction therapy followed by autologous stem cell transplantation, followed by maintenance is considered one line of therapy. A new line of therapy starts when a planned course of therapy is modified to include other treatment agents (alone or in combination) as a result of disease progression, relapse, or toxicity. A new line of therapy also starts when a planned period of observation off therapy is interrupted by a need for additional treatment for the disease. (11)

Appendix E Definition of Relapsed and Refractory Myeloma

Refractory Myeloma:

Refractory myeloma is defined as disease that is non-responsive (failure to achieve minimal response or develop PD while on therapy) while on primary or salvage therapy, or progresses within 60 days of last therapy. There are 2 categories of refractory myeloma.

- **Relapsed and refractory myeloma:**

Relapsed and refractory myeloma is defined as disease that is non-responsive while on salvage therapy or progresses within 60 days of last therapy in patients who have achieved minimal response or better at some point previously to then progressing in their disease course.

- **Primary refractory myeloma:**

Refractory myeloma is defined as disease that is non-responsive in patients who have never achieved minimal response or better with any therapy. It includes patients who never achieve MR or better in whom there is no significant change in M protein and no evidence of clinical progression; as well as primary refractory, progressive disease where patients meet criteria for true progressive disease.

Relapsed myeloma:

Relapsed myeloma is defined as previously treated myeloma which progresses and requires the initiation of salvage therapy but does not meet the criteria for either primary refractory myeloma or relapsed and refractory myeloma. (11)

Appendix F Staging Criteria

Table 11 - Staging criteria for multiple myeloma

STAGE	Criteria
I	Serum β_2 – microglobulin < 3.5 mg/L Serum albumin ≥ 3.5 g/dL
II	Not stage I or III*
III	Serum β_2 – microglobulin ≥ 5.5 mg/L

* There are two categories for Stage II,

- Serum β_2 – microglobulin < 3.5 mg/L and serum albumin < 3.5 g/dL.
- Serum β_2 – microglobulin 3.5 mg/L to < 5.5 mg/L irrespective of the serum albumin.

Appendix G Definitions of Infusion Associated Reactions (IARs)

Table 12 - Types of infusion associated reactions^a

Anaphylaxis
Acute coronary syndrome
Cytokine release syndrome
Drug hypersensitivity
Infusion related reaction

^a This list is not intended to be exhaustive

Table 13 - Symptoms typically associated with infusion associated reactions^a

Abdominal pain	Head discomfort	Pyrexia
Apnoea	Hoarseness	Respiratory distress
Bronchospasm	Hot flush	Rhinitis
Chest discomfort	Hypertensive crisis	Rhinorrhoea
Chest tightness	Hypoxia	Stridor
Chills	Influenza like illness	Tachycardia
Cough	Injection site pain	Throat irritation
Dizziness	Lacrimation increased	Tracheal stenosis
Dysgeusia	Laryngospasm	Tremor
Dyspnea	Myalgia	Urticaria
Feeling hot	Nasal congestion	Vision blurred
Flushing	Nausea	Vomiting
Headache	Pruritus	Wheezing

^a This list is not intended to be exhaustive

Appendix H Revised equations for estimated GFR in Japanese

eGFR (mL/min/1.73 m²) = 194 x Serum creatinine^{-1.094} x Age^{-0.287} x 0.739 (if female). (16)

Web site of Japan Association of Chronic Kidney Disease Initiative:

<http://j-ckdi.jp/ckd/check.html>

Appendix I CD38 blood test interference guideline AABB2016

Advancing Transfusion and
Cellular Therapies Worldwide

Association Bulletin #16-02

Date: January 15, 2016
To: AABB Members
From: ██████████—President
██████████—Chief Executive Officer
Re: Mitigating the Anti-CD38 Interference with Serologic Testing

Summary

A new class of therapeutic agents for multiple myeloma, CD38 monoclonal antibodies, can result in interference with blood bank serologic tests and thereby cause delays in issuing Red Blood Cell (RBC) units to patients receiving these agents. To minimize these delays, hospitals should set up procedures to inform the transfusion service when patients start receiving these agents. Considerations for the transfusion service, both before and after initiation of anti-CD38 therapy, are detailed below.

The AABB Clinical Transfusion Medicine Committee has developed this bulletin to provide background information and guidance to members regarding anti-CD38 interference with serologic testing. The bulletin includes recommendations for its prevention and treatment.

Association Bulletins, which are approved for distribution by the AABB Board of Directors, may include announcements of standards or requirements for accreditation, recommendations on emerging trends or best practices, and/or pertinent information. This bulletin contains information and recommendations. No new standards are proposed.

Background

CD38 monoclonal antibodies are a new treatment for multiple myeloma

CD38, an integral membrane protein that is highly expressed on myeloma cells, has been identified as an effective target antigen for monoclonal antibody therapies. In November 2015, the first therapeutic CD38 monoclonal antibody [daratumumab (Darzalex, Janssen Biotech, Horsham, PA)] was approved by the Food and Drug Administration.¹ Other CD38 monoclonal antibodies are under development.

CD38 monoclonal antibodies interfere with blood bank serologic tests

CD38 is weakly expressed on red cells. Anti-CD38 binds to CD38 on reagent RBCs, causing panreactivity in vitro.^{2,3} Plasma samples from anti-CD38-treated patients consistently cause positive reactions in indirect antiglobulin tests (IATs), antibody detection (screening) tests, antibody identification panels, and antihuman globulin (AHG) crossmatches. Agglutination due to anti-CD38 may occur in all media (eg, saline, low ionic strength saline, polyethylene glycol),

and with all IAT methods (eg, gel, tube, solid phase). Agglutination reactions caused by anti-CD38 are usually weak (1+), but stronger reactions (up to 4+) may be seen in solid-phase testing. However, anti-CD38 does NOT interfere with ABO/RhD typing or with immediate-spin crossmatches.

Other notes on anti-CD38 serologic interference:

- Adsorptions using either untreated or ZZAP-treated cells fail to eliminate the interference.
- Anti-CD38 variably interferes with direct antiglobulin tests (DATs) and antibody identification panel autocontrols.
- Some rare Lu(a–b–) cells are not reactive in the presence of anti-CD38, potentially giving the false impression that the patient has a Lutheran-related antibody.^{4,5}
- Positive IATs can be observed for up to six months after anti-CD38 is discontinued.^{1,3}
- Anti-CD38 may cause a small decrease in hemoglobin in vivo (~1 g/dL), but severe hemolysis has not been observed among treated patients.^{3,6}

Anti-CD38 interference can cause delays in issuing RBCs

If the transfusion service is unaware that a patient has received anti-CD38, the following scenario may occur when the patient's sample is tested:

1. ABO/RhD typing: no issues.
2. Antibody detection (screening) test: all cells positive.
3. Antibody identification panel: all cells positive (autocontrol may be negative).
4. DAT: positive or negative.
5. AHG crossmatches: positive with all RBC units tested.
6. Adsorptions: panreactivity cannot be eliminated.

This leads to delays in issuing RBCs to the patient. In some cases, the anti-CD38 interference could mask the presence of a clinically significant alloantibody.

Recommendations

To avoid problems with transfusion, hospitals should set up procedures to inform the transfusion service whenever any patient is scheduled to begin taking anti-CD38.

BEFORE a patient begins taking anti-CD38:

- A baseline type and screen should be performed.
- In addition, a baseline phenotype or genotype is recommended.

AFTER a patient begins taking anti-CD38:

- ABO/RhD typing can be performed normally.
- For antibody detection (screening) and identification, dithiothreitol (DTT)-treated cells can be used to eliminate the interference.^{2,7}
 - Because DTT treatment destroys Kell antigens, K-negative units should be provided unless the patient is known to be K-positive.
 - Antibodies against other DTT-sensitive blood group antigens (anti-k, anti-Yt^a, anti-Do^a/Do^b, etc) will not be detectable when the antibody screen with DTT-

treated cells is performed; such antibodies are encountered infrequently, however.

Crossmatch

- For patients with a negative antibody screen using DTT-treated cells, an electronic or immediate-spin crossmatch with ABO/RhD-compatible, K-matched units may be performed.
- For patients with known alloantibodies, phenotypically or genotypically matched RBC units may be provided.^{6,8}
 - As some typing antisera require the use of AHG, phenotyping should be performed before the patient receives anti-CD38.
 - Genotyping can be performed either before or after the patient receives anti-CD38.
 - AHG crossmatches with phenotypically or genotypically matched units will still be incompatible.
 - Some clinically significant antibodies may be missed with the use of uncrossmatched phenotypically or genotypically matched units, although this will occur infrequently.
- Alternatively, an AHG crossmatch may be performed using DTT-treated donor cells.
- If an emergency transfusion is required, uncrossmatched ABO/RhD-compatible RBCs may be given per local blood bank practices.

Future/alternative approaches to mitigating the anti-CD38 interference

It is possible to neutralize anti-CD38 in plasma and eliminate the interference using either recombinant soluble human CD38 or daratumumab idiotype antibody.^{2,3} Neither reagent is widely available at this time, and additional validation would be needed. In principle, soluble CD38 could be used to neutralize any anti-CD38, while different idiotype antibodies would be needed to neutralize different CD38 therapeutic antibodies. Finally, antigen-typed cord cells have been used for the antibody screen as an alternative to DTT-treated cells.⁹

References

1. Darzalex package insert. Horsham, PA: Janssen Biotech, 2015. [Available at: <http://www.darzalex.com/shared/product/darzalex/darzalex-prescribing-information.pdf> (accessed January 7, 2016).]
3. Oostendorp M, Lammerts van Bueren JJ, Doshi P, et al. When blood transfusion medicine becomes complicated due to interference by monoclonal antibody therapy. *Transfusion* 2015;55(6pt2):1555-62.
